The third time-varying variable that was piloted is the response/nonresponse criteria after Step One. Of the 49 patients across both pilot studies who completed an assessment after Step One, 38 (77.6%) responded after Step One (see b.2. for responder status criteria). Congruency between responder status criteria and parents’ thoughts about if more treatment was needed was as follows: 75.5% congruent, 20.4% incongruent (with one parent wanting to end when more treatment was recommended), and 4.1% unsure. As per our pilot protocol, parents who think more treatment is needed after Step One are offered two additional sessions, and if a child relapses after the maintenance phase, they can step up (no child stepped up after the post-assessment). Given these results, we will use the same responder status criteria derived from our pilot work.

**c.1.4. Cost Measures and Preliminary Costs of Delivering Stepped Care and TF-CBT.** The R34 stepped care grant: 1) piloted data collection methods on the costs of delivering SC-TF-CBT and TF-CBT, and 2) conducted a preliminary comparison of costs associated with delivering SC-TF-CBT and TF-CBT. These cost methods were incorporated into the SC-TF-CBT trial with older children. 1) *Costs Characteristics Information (CCI)*[82] consists of 11 items to measure estimated costs such as out-of-pocket expenses for treatment, lost income due to missing work to attend therapy, patient time associated with treatment, and other cost-related information. We have been successful capturing these cost-related data and procedures for collecting missing data regarding parent’s co-pay have been established. 2) *The Therapist/Patient Time Tracking System (TTTS)*[83] measures the therapist time associated with 14 types of treatment delivery activities (e.g., therapist meetings, phone support, documentation) and parent/child time associated with 9 types of treatment participation (e.g., therapist meetings, phone support, homework). The Service Assessment for Children and Adolescents (SACA)[84] will be administered to track other services used and estimated costs of other services. These cost measures will be used in the proposed study to address the next important step of examining the economic cost of delivering SC-TF-CBT and standard TF-CBT (Aim 4). Also, if tailoring variables effectively distinguish child

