## STUDY DESIGN AND SAMPLE SIZE

**c.4. Design/Randomization.** Participants (N=216, ages 4-12) are randomized and will receive SC-TF-CBT or TF-CBT in a 1:1 ratio within community-based agencies. To ensure the two treatment conditions are balanced in regard to candidate first-stage tailoring variables, a randomized block design will be used. Based on pilot results (see c.1.3.), we will divide our sample into four cells based on whether the child has internalizing T-scores > or ≤71 and whether s/he has a critical life events score > or ≤16. Each cell will have equal numbers of children assigned to SC-TF-CBT and TF-CBT. See “Other Attachment” for study timeline.

**c.4.1. Design Considerations. Why not conduct a Sequential Multiple Assignment Randomized Trial (SMART) to build the adaptive intervention?**[34, 89] **1)** The adaptive SC-TF-CBT has been developed [4-6] and is at the developmental stage of comparing it to the standard in the field (i.e., TF-CBT). Many of the questions that would have been examined in a SMART, such as effectiveness with different ages,[25, 90, 91] different types of traumas,[25, 63, 92] different components and different lengths,[26] and with and without medication[93] have consistently suggested that standard TF-CBT is the recommended treatment. **2)** Our pilot studies, designed to inform this R01 application, documented that a first-line parent-led approach is feasible and acceptable, identified an estimated number of Step One responders, demonstrated the clinical utility of the responder status criteria, and identified candidate first-stage tailoring variables and second stage time-varying tailoring variable. Thus, there is ample evidence for testing the confirmatory stage of an optimized adaptive intervention with a randomized clinical trial in community settings. **3)** In order to re-randomize after non-response there typically needs to be least 35% to 65% non-responders,[94] and our preliminary data after Step One indicate that 22% were non-responders. Once the first-stage tailoring variables are identified and children can be matched to appropriate treatment at baseline, we anticipate that the Step One non-response rate would be even less.

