**Primary Aim 2:** To examine tailoring variables that could be used to individualize the decision of which children should be assigned at baseline to SC-TF-CBT versus standard TF-CBT, we will compare the responders/non-responders of Step One with regard to the value of the tailoring variables. Based on results from pilot studies, we hypothesized that children with more internalizing problems at baseline and those from families with potential life event barriers are less suitable for SC-TF-CBT. A Chi Square test will be first applied to evaluate the association between the dichotomized candidate tailoring variable and responding status. Next, we will use GLM, in which responding status will be treated as the dependent variable and tailoring variables as continuous predictors. To further quantify the relation between the value of the tailoring variables and the propensity of not responding to Step One, we will include in the GLM the products of the tailoring variables to evaluate their interactions. Demographics will also be controlled in the model. While it was not a primary aim, we will further explore whether race/ethnicity or gender moderate the dropout rate and treatment outcomes (see 6.). This will be done in a separate analysis where interactions with treatment condition are included.

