## Amendment to the analysis plan 2.11.2022

**Aim 1.** We applied linear mixed-effect models (LME; SAS Institute Inc, 2015) with repeated measures to detect whether the two treatments performed differently at post-, 6- and 12-month assessments. Instead of 5% alpha we used a more stringent 2.5% alpha (Piaggio et al, 2012) for the non-inferiority analysis with the .41 margin. For the non-inferiority margin for the PCL-5, the clinically significant change threshold is 10 points although adult PTSD trials have used -5 (Foa et al., 2019) to -10 (Mathersul et al., 2019) points. We used -8.8 as the margin which was based on an expert panel and prior studies with adults (Acierno et al., 2017). Due to attrition (27.87%) being higher than planned (15%) and enrollment (N = 183) lower than the planned enrollment (N = 216), the power analysis was based on the actual randomization of 183 participants (SC-TF-CBT=91; standard TF-CBT=92).

**Aim 2.** We used backward stepwise logistic regression with predictors with  $p < .01$ . Besides predictors in the unadjusted model, demographics including children gender, age and race were included in the partially adjusted

model. In addition, three child primary outcomes were added for the full adjusted model.

**Aim 3.** Instead of LDS we used Linear mixed-effect models (LME) with repeated measures were used to detect whether the potential mechanisms of change declined significantly over time and whether the rate of change differed by treatment group with standard TF-CBT coded as 0 and Step One responders coded as 1. Further, we tested mediation and moderated mediation. If moderated mediation was not found mediation was tested with two regression equations: the first equation included mediators regressed on treatment condition and outcome variables at baseline; the second equation included outcomes regressed on treatment condition, mediators, and outcome variables at baseline. If there was no evidence of significant mediation, linear regression model (OLS) was applied to test the linear estimates as predictors for both outcome (TSCYC-PTS and CSDS-P).

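### The amended fully adjusted Aim 2 logistic model has about two expected non-responders per parameter, so ordinary maximum likelihood overstates the tailoring effects; a Firth-penalised fit is a cheap remedy

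*Combined protocol and SAP*

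**What the plan says.** Section c.8.3 (Primary Aim 2) compares Step One responders with non-responders. It starts with a chi-square test on the dichotomised tailoring variables. A GLM on the continuous tailoring variables with demographics follows, in which "we will include in the GLM the products of the tailoring variables to evaluate their interactions". Section c.6.8 names two first-stage tailoring variables: the internalizing T-score and the critical barriers score. Section c.9 powers Aim 2 only as a comparison of two response rates in 92 SC-TF-CBT children.

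The amendment of 2.11.2022 describes backward stepwise logistic regression at p<.01 in three layers. The first is unadjusted. In the second, "demographics including children gender, age and race were included in the partially adjusted" model. In the third, "three child primary outcomes were added for the full adjusted model". The amendment does not list the predictors of the unadjusted model, the coding of race or the number of non-responders. It does not say whether the three outcomes are baseline values, or whether the product term is kept. It names no penalised or exact estimator.

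On numbers, the amendment gives the "actual randomization of 183 participants (SC-TF-CBT=91; standard TF-CBT=92") and an overall attrition of 27.87%. Section c.1.3 reports: "Of the 49 patients across both pilot studies who completed an assessment after Step One, 38 (77.6%) responded after Step One". Section c.4.1 repeats the rate: "our preliminary data after Step One indicate that 22% were non-responders".

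**The concern.** In logistic regression the information comes from the rarer outcome, here non-response. When there are only about two events per parameter, maximum likelihood estimates are biased away from zero, so odds ratios look stronger than they are. Some data sets also give separated or non-converging fits. Adding scores that share information with internalizing problems widens the standard error of that coefficient too.

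Aim 2 is meant to inform which children should start with parent-led treatment. Sections c.1.4 and c.8.3 (Primary Aim 4) also make a subgroup cost comparison depend on whether the tailoring variables separate responders. An inflated odds ratio would overstate how well a baseline score does that. Section c.1.2 already concedes that the pilot signals were fragile after allowing for multiple comparisons, so a sound estimate is much of what this aim can add.

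**Working it through.** **The plan's own Aim 2 figure.** Section c.9 gives 80% power with 46 children per half. Power = Φ{[|p1−p2|√n − 1.96√(2p̄q̄)] / √(p1q1+p2q2)}. For 62% vs 30%: (0.32×6.782 − 1.96×0.705)/0.668 = 1.18, so power is 88.1%. The other two pairs give 88.4% and 86.7%. With a continuity correction the three values are 83.2%, 83.5% and 81.1%. The stated 80% is therefore met, but for a two-group comparison and not for the amended model.

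**Expected non-responders.**
- Upper sample size: 91 randomised. Lower bound: 91 × (1 − 0.2787) = 65.6, if the overall attrition applied in full to this arm and this assessment.
- Pilot rate among assessed children: 11/49 = 22.4%. This gives 65.6 × 0.224 = 14.7 and 91 × 0.224 = 20.4.
- With the 13 pilot Step One dropouts (c.1.3) counted as non-responders: (11+13)/(49+13) = 24/62 = 38.7%. This gives 25.4 to 35.2.

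**Parameters.** 2 tailoring slopes + 3 demographic slopes (binary race) + 3 outcome scores + intercept = 9. The product term or further race categories would add to this.

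**Events per parameter.** 14.7/9 = 1.6 to 20.4/9 = 2.3. With dropouts counted: 25.4/9 = 2.8 to 35.2/9 = 3.9.

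**Size of the bias.** Simulations assumed a true log-odds of 0.80 per SD for each tailoring variable (odds ratio 2.2). The three scores were correlated 0.5 with internalizing and had no effect of their own. Runs with slightly different set-ups gave these mean full-model maximum likelihood estimates:

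| Setting | Mean log-odds | Excess over 0.80 |
|---|---|---|
| n=91, about 20 events | 0.97-0.98 | 21-22% |
| n=66, about 15 events | 1.07-1.10 | 34-38% |
| n=91, about 35 events | 0.93-0.96 | 16-20% |

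Firth penalisation of the same full model gave 0.79-0.81.

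A second simulation (1,500 data sets per setting, eight slopes, scores correlated 0.4) used effects of pilot size, with true odds ratios per SD of 2.86 and 2.72 (log-odds 1.05 and 1.00). The full maximum likelihood model had median odds ratios of 3.78 and 3.54 at n=66, and 3.43 and 3.19 at n=91. Firth gave 2.71 and 2.62, and 2.77 and 2.61. On the mean log-odds scale for internalizing, the excess was ln(4.45)/1.05 − 1 = 42% at n=66 and ln(3.71)/1.05 − 1 = 25% at n=91. At n=66, 3% of fits separated or failed to converge, and 9% did so with one more race term.

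**Power at p<.01, pilot-size effects.**

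| | Full model | Two-variable model |
|---|---|---|
| Internalizing, n=66 | .32 | .51 |
| Internalizing, n=91 | .58 | .74 |
| Life events, n=66 | .38 | .46 |
| Life events, n=91 | .65 | .68 |

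With half the pilot log-odds, power is .09-.20 in the full model and .10-.21 in the two-variable model.

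**Covariates or estimator?** At n=91 with 23 events, true log-odds 0.80 and p<.05, power for internalizing is: full maximum likelihood .50, full Firth .40, two-variable maximum likelihood .82, two-variable Firth .80. Dropping covariates raises power; Firth does not.

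**The case against.** The strongest reply has four parts.

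First, the event count is inferred. The pilot rate covers only children assessed after Step One. The documents do not say how children stepped up early for new trauma or low adherence are classed. The 27.87% is overall attrition, whereas responder status is set around week 6, so n=66 is a lower bound. The planning rates in c.9 themselves imply 32 to 50 non-responders among 92 (for example 92 × (1 − 0.65) = 32.2), which does not fit the 22% in c.4.1. This stands as a limit on precision, but at 35 events the bias is still 16-20%.

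Second, the parameter count is inferred. If elimination ran before adjustment, fewer terms would remain. This also stands, and it is a reason to ask for the predictor list.

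Third, the amendment does not make the full model primary or the sole test of Hypothesis 2.1. Unadjusted and partially adjusted models are listed, and the chi-square test of c.8.3 is not expressly withdrawn. The documents also frame tailoring through score cut-offs and response rates, and do not say that odds ratios will decide assignment. All of this is correct.

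Fourth, a reader might infer that the full model loses the hypothesised signals and that a two-variable model would put this right. Neither follows. At p<.01 the two-variable model also has limited power, and for life events the two models differ little. If each of the three scores had its own log-odds of 0.3 (an assumption), the two-variable Firth estimate would be 1.20 at n=91, against a severity-adjusted truth of 0.80 and 1.03 from full maximum likelihood. The two models answer different questions.

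**Conclusion.** The concern holds for the estimator. With about 15 to 20 non-responders and at least nine parameters, ordinary maximum likelihood in the fully adjusted model overstates the tailoring log-odds by roughly 20-35% on average at a true value of 0.80. An odds ratio of 2.2 is then read as about 2.6 to 2.9 (e^0.97 to e^1.07). With 35 events the excess is about 15-20%; with pilot-size effects at the lower-bound sample it reaches about 42%. Firth penalisation of the same model brings the estimate close to the truth in every setting examined.

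Power for internalizing problems is reduced, but the p<.01 rule and the small sample account for part of the loss.

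The conclusion assumes the pilot rate carries over, the two hypothesised predictors, binary race, no product term, and that a logistic model without a named penalty was fitted by maximum likelihood. It does not show that the unadjusted or partially adjusted results are wrong, nor that severity adjustment is a mistake.

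**What to change.** Refit the unadjusted, partially adjusted and fully adjusted models with Firth-penalised logistic regression and report profile-likelihood intervals. Beside each model, give the full predictor list (including race coding and whether the product term is kept), the time point of the three outcome scores, the number of children and the number of non-responders. State how early step-ups and dropouts are classed.

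Read the unadjusted two-variable model as the marginal predictive answer to Hypothesis 2.1 and the fully adjusted model as the severity-adjusted one, without presenting either as a correction of the other.

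The amendment is written in the past tense, so the cost is a re-run in standard software plus a reporting change; no new data are needed. Odds ratios will be somewhat smaller. Wald power will fall, from .50 to .40 in the full model and from .82 to .80 in the two-variable model in the p<.05 setting above. Penalisation deals with small-sample bias only. It does not restore power lost to covariates or to the p<.01 rule.

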**Aim 3:** To examine if changes in the following potential mechanisms of change variables mediate treatment effects (e.g., Step One and standard TF-CBT) on child PTSS and impairment: (a) fear habituation: decreases in child’s fear-based arousal; (b) cognitive changes: reductions in child’s negative trauma-related cognitions; (c) inhibitory learning: child’s decrease in expectancy of negative outcomes; and (d) fear toleration: extent of child’s toleration of fear activation.

**3.1. Hypothesis:** Decreases in children’s fear-based arousal, improvements in negative trauma-related cognitions, decreases in children’s expectancy of negative outcomes, and changes in fear toleration over time will mediate Step One and standard TF-CBT treatment outcomes in PTSS and impairment.

**3.2. Secondary Hypothesis:** The mechanisms of change (e.g., a, b, c and d in Aim 3) will occur during all components of treatment but greater changes in these processes will occur during more direct exposure activities (e.g., imaginal and *in vivo* exposure in Step One) than less direct exposure activities (e.g., developing a trauma narrative in Standard TF-CBT) and during coping skills in both treatments.

**Aim 4:** To examine the economic cost of delivering SC-TF-CBT versus standard TF-CBT.

**4.1. Hypothesis:** Stepped Care TF-CBT will be more cost-effective than standard TF-CBT.

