feedback. *Stepping Together*, written on a 6th grade level, provides a step-by-step approach for parents to provide treatment at-home with 11 parent-child meetings. Weekly phone support is provided for support, coaching and motivation. Pilot data suggest that ~89% of scheduled phone calls occurred. When calls did not occur, the therapist or parent would leave a message confirming the next time available to talk. There is also a *Stepping Together* website with two video demonstrations (see Appendix). Step Two is therapist-led and consists of 9 weekly (90 minute) TF-CBT therapy sessions [62, 63](see c.3.1.).

After completing Step One, a brief assessment occurs. If responder status is met, the parent and child end treatment and proceed to the Maintenance phase which is designed to further open parent-child communication and encourage the parent and child to use the tools that they learned in Step One. Responder status criteria was developed and tested in the pilot studies.[7] Establishing responder status involves three methods of measuring treatment response/nonresponse: 1) a semi-structured interview (with parents for young children ages 4-6 and with parents and children for children ages 7-12) about PTSD symptoms. Responders must have 3 or fewer symptoms for younger children and 4 or fewer symptoms for older children. The one symptom difference is based on prior research on PTSD with young children that documented that fewer symptoms are needed for young children to meet criteria[64] and recent differences in number of symptoms needed for PTSD diagnosis based on age according to DSM-V[65]; or 2) below the clinical cut off score on a continuous measure of PTSD symptom severity (completed by parents for young children and by the child for older children); and 3) a rating of 3 (improved), 2 (much improved), or 1 (free of symptoms) on the Clinical Global Impression–Improvement scale (CGI-I)[66] that takes into account impairment. Results from our pilot data on SC-TF-CBT suggest even before responder status is determined, there are two additional second-stage tailoring variables (e.g., non-compliance and concurrent trauma exposure) that should indicate a “trigger and switch” approach to an immediate step-up to Step Two (see c.1.3.).

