**c.1.3. Time-Varying Stage Two Tailoring Variables and Step One Responder Status.** Based on our pilot data, we are proposing to incorporate into SC-TF-CBT two new time-varying tailoring variables that may occur during stage-one treatment that will lead to a “trigger and switch” approach. **1) Child exposed to a new traumatic event after baseline assessment.** In the R34 study, Step One non-responders experienced significantly more new traumatic events than Step One responders (92% vs. 36%, Fisher’s exact test,  $p<.001$ ). When a new traumatic event occurred during the parent-led treatment, it was challenging for the parent and child to process the additional trauma thus indicating that more intensive therapist-led treatment (i.e., Step Two) was needed. TF-CBT has established methods for working with children with on-going traumas.[81] **2) Early non-adherence to Step One.** We had a three-step noncompliance process which involved problem-solving, allowing additional weeks for making up activities, and stepping up if significant progress completing Step One was not being made. Six of 13 Step One dropouts only attended the 1st therapist meeting. The therapists made numerous follow-up calls to problem-solve, and additional time to complete activities before scheduling the 2nd therapist meeting was allowed. Additional time did not result in adherence. We have carefully re-considered the non-compliance protocol and developed a revised non-adherence plan that will allow for early identification of non-compliance. During the phone meetings, therapists will encourage parents to complete the parent-child meetings and problem-solve if meetings are not occurring. The 2nd therapist meeting will not be postponed if the parent-child meetings were not completed. Instead, the therapist will review adherence (see c.6.7.) and if  $< 75\%$  is completed, the child will be stepped up to therapist-led treatment. Some parents may not be able to lead treatment due to various reasons including uncertainty or their own emotional reactions; thus, more quickly stepping-up treatment may minimize drop outs.

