### **c.3. Treatment Conditions INTERVENTIONS PROVIDED**

**c.3.1. Treatments.** Each treatment will be provided over 12-14 weeks, although flexibility will be allowed to minimize drop out. SC-TF-CBT patients will receive Step One: 3 (1 hr.) in-office therapist-led sessions over 6 weeks, the parent-child workbook (*Stepping Together*),[60, 61] scheduled weekly phone meetings (15 minutes), and information from the Stepping Together website and the National Center for Childhood Traumatic Stress website (via web or paper for those without access). Children who do not meet responder status will receive Step Two: 9 (1.5 hr.) in-office therapist-directed sessions of TF-CBT over 6 to 8 weeks. Standard TF-CBT patients will receive 12 (1.5 hr.) standard weekly in-office therapist-directed sessions (2 additional weeks allow for scheduling difficulty). TF-CBT includes child, parent and conjoint parent-child sessions addressing the 10 core trauma treatment components of TF-CBT (e.g., parenting skills, affect modulation, cognitive coping, trauma

narrative, etc.).[87] Is early termination of Step Two possible? For patients receiving step two TF-CBT, 9 sessions will be provided. However, in some cases, early termination may be possible. If two consecutive CGI-I parent and therapist ratings independently indicate a 2 (much improved), or 1 (free of symptoms) and the child is not in the middle of the trauma narration or conjoint component, the TSCYC-PTS total will be administered. If there is a 40 or less on the PTS total on the TSCYC measure, a post assessment with the IE may be scheduled. If responder status is met, the therapist will discuss with the parent the option of an early termination or continuing treatment. If treatment ends early, a final termination session may occur to discuss progress and relapse prevention. If the responder status is not met, the child will complete the step two treatment and there will be a post assessment upon completion.

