change in HR and SC responses to the interview relative to baseline. 2) A subjective unit of distress (SUD) scale which is commonly used will be rated by the child using a developmentally appropriate SUD rating (i.e., “scary feeling score,” 0-3 or 4). Prior research with young children as well as our experience suggests that children age 4 and older understand the rating scale and can provide these data. Similar to our pilot work, children will provide six ratings during exposure or trauma-related activities and parents will record these ratings. In TF-CBT, the child ratings will be recorded by the therapist. The first rating will occur before the exposure/activity, four during the activity with the highest being recorded as the peak rating and one after the exposure/activity. Changes in trauma-related negative appraisals: The *Post-Traumatic Cognitions Inventory-child version (CPTCI)*, is a 25-item child report of negative trauma-related cognitions. The CPTCI has demonstrated excellent psychometrics and no age-related differences in scores for children ages 6-18. The measure will be administered with children ages 6 to 12 (~78% of the sample). Expectancy of negative outcomes (ENOs): The ENOs measure, modified from [name] et al. and similar to Deacon et al., is a 3-item parent report of the child’s perceived expectancy of a negative outcome that is rated (0 to 100) before and after the trauma-related activity. Children’s fear toleration (CFT): Similar to Deacon et al., parents will rate (0-100) the extent of the child’s fear toleration when participating in the trauma-focused activity. Therapeutic worry and alliance will also be examined as potential mechanisms of change which will be measured using the treatment worry questionnaire at baseline only (child and parent version) and the Therapeutic Alliance Scale for Children (TASC, parent, child, and therapist version) administered the same assessment time periods as the HR and SC (i.e., Weeks, 0, 2,4 = Step One & 0,5,8= TF-CBT and at post-assessment) (Keeley et al. 2011). As indicated in Table 1, the mechanism of change measures will occur at post-assessment too. The “trauma-related activity” will be a 5 minute semi-structured interview that consists of the same guide that is used during the HR and SK test. After these measures are completed the parent and child will be asked independently 6 questions about their experiences talking about what happened, including how they may have changed. These responses will be used to triangulate the quantitative measures.

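### The amended Aim 3 slope models set standard TF-CBT against Step One responders only, so the group-by-time contrast is not randomised and favours Step One for any mechanism whose improvement goes with response

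*Combined protocol and SAP*

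**What the plan says.** The Aim 3 paragraph of the amendment of 2.11.2022 tests whether each mechanism declined over time and "whether the rate of change differed by treatment group with standard TF-CBT coded as 0 and Step One responders coded as 1". It gives no code for Step One non-responders or for children stepped up early. It gives no reason for using responders, and no analysis of the whole SC-TF-CBT arm.

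Section b.2 places the responder decision at a brief assessment after Step One. It rests on an interview symptom count, or on being "below the clinical cut off score on a continuous measure of PTSD symptom severity", together with a CGI-I rating. Section c.6.8 lists the TSCYC among the instruments for responder status, and TSCYC-PTS is also an Aim 3 outcome in the amendment.

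Section b.2 adds that "even before responder status is determined, there are two additional second-stage tailoring variables", and c.1.3 describes them: "Child exposed to a new traumatic event after baseline assessment", and early non-adherence to Step One. Either leads to an immediate move to Step Two. Section c.1.3 also reports that in the R34 pilot "Step One non-responders experienced significantly more new traumatic events than Step One responders" (92% against 36%).

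Randomisation was between SC-TF-CBT and standard TF-CBT, 1:1 within four cells defined by internalizing T-score and critical life events (c.4). The Aim 3 text in c.8.3 concerns Step One and TF-CBT, and c.9 powers Aim 3 on 184 children in both conditions. Hypothesis 3.1 states that changes in the mechanisms "will mediate Step One and standard TF-CBT treatment outcomes in PTSS and impairment".

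**The concern.** The standard TF-CBT group contains children who do well and children who do badly. The Step One group, as coded, contains only those who did well enough to be called responders, judged partly on a measure of the Aim 3 outcome itself. Children in SC-TF-CBT who met a new trauma or fell behind on the parent-led work leave the coded group. Children in standard TF-CBT who met a new trauma do not.

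If both treatments move a mechanism equally, this coding can still show faster improvement under Step One whenever that mechanism is linked to response. A true Step One disadvantage could be hidden in the same way. A reader would see a difference by treatment group from a randomised trial and take it for a randomised comparison of how the two treatments work.

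**Working it through.** **Checks on the documents' own figures.** 216 × 0.85 = 183.6, the 184 of c.9. 38/49 = 77.6%, the Step One response rate in c.1.3. In c.1.2, 56.3% of 16 is 9 and 87.9% of the other 33 is 29; 9 + 29 = 38, and the uncorrected chi-square for 9/16 against 29/33 is 6.19, as printed.

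**Inputs.** From the documents: 91 children randomised to SC-TF-CBT and 92 to standard TF-CBT (amendment), and the pilot response rate of 77.6%. Assumed, because no document gives them: the correlation ρ between a child's mechanism slope and response, the reliability of the slopes, and that the pilot response rate applies in this trial.

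**Bias.** Treat response as the top share p of a standard normal variable that has correlation ρ with the slope. With no true difference between arms, the expected excess in responders, in slope SD, is

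bias = ρ × φ(z) / p, where z is the normal quantile at 1 − p.

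At p = 0.776, z = −0.757, φ(z) = 0.2995 and φ(z)/p = 0.386.

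| ρ | Bias (slope SD) | Rejection, slope reliability 0.5 | Rejection, error-free slopes |
|---|---|---|---|
| 0 | 0 | 5% | 5% |
| 0.3 | 0.12 | about 8% | about 12% |
| 0.5 | 0.19 | about 14% | about 24% |
| 0.7 | 0.27 | about 23% | about 43% |

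The rejection columns are simulated rates for a two-sided 5% test under no true difference, with 91 and 92 randomised and therefore about 71 responders (91 × 0.776).

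If the effects of 0.29 and 0.33 (CPTCI) in c.9 are read as this correlation, which is an assumption, the bias is 0.29 × 0.386 = 0.11 to 0.33 × 0.386 = 0.13 SD. Masking works in the same way: at ρ = 0.5, a true Step One disadvantage of 0.20 SD would appear as −0.20 + 0.19 = −0.01 SD.

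**Sensitivity to the responder share.** The 77.6% is among children assessed after Step One. Section c.1.3 also mentions 13 Step One dropouts.

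| Responder share | φ(z)/p | Bias at ρ = 0.3, 0.5, 0.7 |
|---|---|---|
| 38/49 = 77.6% | 0.386 | 0.12, 0.19, 0.27 |
| 38/(49 + 13) = 61.3% | 0.625 | 0.19, 0.31, 0.44 |
| 38/(57 + 9) = 57.6% | 0.680 | 0.20, 0.34, 0.48 |
| 50% (assumed) | 0.798 | 0.24, 0.40, 0.56 |

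The second row assumes that the dropouts are additional to the 49. The third uses the 57 randomised and 9 open-trial children in c.1 as starters. The new-trauma trigger was not part of the pilot rule and could lower the share further: 36% of R34 responders had a new event, and if all of these fell within Step One (the window is not stated) the share would be 0.776 × 0.64 = 50%. No upper bound follows from these figures.

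**Baseline balance.** In the pilot, 16/49 = 32.7% of assessed Step One children had internalizing T above 71, against 9/38 = 23.7% of responders. Selecting responders can therefore undo the balance that the blocking in c.4 was meant to secure. This is only suggestive, because the cut-off was chosen in that small sample to separate responders.

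**Time scale.** Table 1 schedules HR, SC and CPTCI at weeks 0, 2 and 4 in Step One and 0, 5 and 8 in TF-CBT. If total change D by the third assessment is equal, the weekly slopes are D/4 and D/8. Step One then has twice the slope from the coding of time alone.

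**The case against.** The best defence is that the amendment names the group openly, never calls the contrast randomised, and may only describe how responders changed. There is also a plausible reason for the choice, although none is stated. Section c.3.1 says "Children who do not meet responder status will receive Step Two", and c.6.5 says "the mechanism of change measures will occur at post-assessment too", so a non-responder's post-assessment value mixes both steps. That supports cutting those children's series at step-up. It does not support dropping their Step One data, which are scheduled before the week 6 assessment that decides response. The descriptive reading is also hard to hold when the amendment speaks of a difference by treatment group and c.8.3 and c.9 planned Aim 3 on Step One and TF-CBT in both conditions.

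Several limits stand. That non-responders were excluded is read from the two-value coding; the amendment does not say so in words. The adherence trigger concerns parent-led meetings, so it has no exact counterpart in standard TF-CBT. Children who leave for a new trauma need not differ in mechanism change, and a single response threshold does not represent all three filters. The sizes above are illustrations.

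A reader might infer that the mediation results, and hence hypothesis 3.1, are invalid. The documents do not support that: the mediation equations refer to treatment condition without redefining it, and c.8.3 uses that term for the arms being compared.

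**Conclusion.** The concern holds for the amended slope comparison. It is not randomised, and it is biased toward Step One for every mechanism whose improvement is positively associated with response. Hypothesis 3.1 implies such an association, since response is judged on PTSD symptoms and a rating that takes account of impairment. At zero correlation, selection on response adds no bias.

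The size is not known. The 0.12 to 0.27 slope SD at a 77.6% response rate rests on assumed correlations of 0.3 to 0.7, and the rejection rates also rest on assumed slope reliability. A lower responder share makes the bias larger, and no ceiling can be stated.

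Two stronger readings should be avoided. The documents do not show that every mechanism is biased by a known amount. Nor does the problem reach Aim 1, whose amended analysis compares the two treatments and contains no responder restriction. Hypothesis 3.1 is affected only if the mediation models use the same coding, which the plan should settle in one sentence. This should be fixed before the Aim 3 slope results are read as a comparison of treatments.

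**What to change.** 1. Make the main slope contrast all children randomised to SC-TF-CBT, using mechanism data up to the end of Step One or step-up, against all children randomised to standard TF-CBT. Include the two blocking factors as covariates.
2. State the time scale for each measure. For HR, SC and CPTCI, align by the three scheduled assessments. For SUD, ENOs and CFT, which are rated at every session or parent-child meeting, align by treatment component or session order. Do not use calendar weeks alone.
3. Code the mediation and moderated-mediation models by randomised arm, and say so.
4. Keep the responders-only comparison, with its post-assessment data, as an exploratory analysis labelled as non-randomised.

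This needs no new data, only some further analysis. Children who step up or leave early contribute short series, and the main contrast does not use mechanism data collected after step-up. Calendar time stays unequal between the arms (4 against 8 weeks at the third scheduled assessment), which the report should state. Some bias can remain if step-up or dropout depends on change that was not observed. With attrition at 27.87%, that limitation should be reported alongside the result.
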